9.5 Outcomes

A combination of description statistics, pearson correlations, and general linear models (GLM) such as ANCOVA, will be used for analyzing the data.

Assessment	Time Points Collected	Analysis Plan	Section
Demographics, health behaviors, height & weight	Visit 1	Descriptive statistics	9.6
Daily GERD Symptom Diary	Visit 1 & Visit 2	Primary Outcome – ANCOVA analysis adjusting for baseline GERD symptom severity and visit type using follow-up GERD symptoms as the outcome.	9.5.1
GERD-HRQL	Visit 1 & Visit 2	Descriptive statistics and secondary measures of GERD symptom severity in ANCOVA analyses.	9.6
NIH PROMIS GERD			
GSRS			
Current Stress	Visit 1 (both before & after provider visit) & Visit 2	Descriptive statistics and covariate in GLM analyses.	9.6
PSS-10	Visit 1 (before provider visit) & Visit 2	GLM to determine whether perceived stress is a modifying factor for change in GSR and HRV in the context of the visit intervention	9.6
FFI	Visit 1	GLM to determine whether personality is a modifying factor for change in GERD symptoms in the context of the visit intervention	9.6
GSR & HRV	Visit 1	Secondary Outcome – GLM assessing change in GERD symptom severity and physiologic concordance in patient-provider dyads	9.5.1
Video Recording	Visit 1	Secondary Outcomes - GLM to compare the frequency of supportive provider behaviors between the standard and expanded visit groups and responders vs. non-responders (those with a 50% or greater improvement in GERD symptoms).	9.5.2
Impressions of the Study Physician	Visit 1, post-intervention	GLM to determine whether empathy and the patient-provider connection modify change in GERD symptoms in the context of the visit intervention	9.6
CARE			
HEAL Patient-Provider Connection			

9.5.1 Primary Outcome

1. Change in the average daily GERD symptom severity score from baseline to the last week of the study in the expanded vs. standard group. GERD symptom severity is based on the sum of scores assessing the severity of daytime heartburn, nighttime heartburn, and acid reflux each on a 0-4 point scale (none, mild, moderate, severe, very severe; higher scores signify worse symptoms). We will use ANCOVA for the primary analysis, adjusting for baseline GERD symptom severity and visit type assignment using the 8 week follow-up GERD symptom severity as the outcome. Potential moderators that will be assessed in exploratory analyses will include gender (both patient and provider), race, visit length, patient stress, personality type, and perceived connection with/empathy of the provider.

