5. STUDY INTERVENTIONS	18
5.1 Interventions, Administration, and Duration	18
5.2 Handling of Study Interventions	19
5.3 Concomitant Interventions.....	19
5.4 Adherence Assessment	19
6. STUDY PROCEDURES	21
6.1 Schedule of Evaluations for Subjects/Patients.....	Error! Bookmark not defined.
6.2 Description of Evaluations.....	23
6.2.1 Telephone Screening (Day -30 to -7).....	23
6.2.3 Blinding.....	25
6.2.4 Post-Intervention Measures (Day 0)	26
6.2.5 Completion/Final Evaluation	26

7. SAFETY ASSESSMENTS	28
7.1 Specification of Safety Parameters	29
7.2 Methods and Timing for Assessing, Recording, and Analyzing Safety Parameters	29
7.3 Adverse Events and Serious Adverse Events	30
7.4 Reporting Procedures.....	30
7.5 Follow-up for Adverse Events	30
7.6 Safety Monitoring	31
8. INTERVENTION DISCONTINUATION.....	31
9. STATISTICAL CONSIDERATIONS	31
9.1 General Design Issues.....	31
9.2 Sample Size and Randomization	33
9.3 Definition of Populations.....	33
9.4 Interim Analyses and Stopping Rules.....	34
9.5 Outcomes	34
9.5.1 Primary Outcome	36
9.5.2 Secondary Outcomes	36
9.6 Data Analyses	37
10. DATA COLLECTION AND QUALITY ASSURANCE	37
10.1 Data Collection Forms	37
10.2 Data Management	38
10.3 Quality Assurance	38
10.3.1 Training.....	38
10.3.3 Metrics	38
10.3.4 Protocol Deviations.....	38
10.3.5 Monitoring	38
11. PARTICIPANT RIGHTS AND CONFIDENTIALITY	38
11.1 Institutional Review Board (IRB) Review	38
11.2 Informed Consent Forms	39
11.3 Participant Confidentiality	39
11.4 Study Discontinuation.....	39
12. POTENTIAL BENEFITS	40
12.1 Potential Benefits to Participating Individuals	40
13. COMMITTEES.....	40

14. PUBLICATION OF RESEARCH FINDINGS.....	Error! Bookmark not defined.
15. REFERENCES	40
16. LIST OF SUPPLEMENTS/APPENDICES.....	47

STUDY TEAM ROSTER - *key personnel*

[name], PhD, MPH, Principal investigator

[name] [name], Co-investigator

[name], MSc, Co-investigator

[name], MSPH, Co-investigator

PARTICIPATING STUDY SITES

University of California, Davis

Division of General Medicine

[name]

[name]

[contact]

Email: [contact]

PRÉCIS

Study Title: Physiology of GERD and Treatment Response

Objectives

Primary Aim: To determine in a randomized controlled trial (n=60) whether an expanded, compared to a standard, provider visit can augment the effects of a medication targeting traditional or functional GERD symptoms.

Secondary Aims:

1. To identify physiologic markers of enhanced therapeutic relationships.

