2. To identify patient and physician behaviors associated with GERD symptom improvement.

Design and Outcomes

This is a randomized controlled trial to assess the physiologic and behavioral mechanisms associated with augmented medication effects in adult patients with functional GERD-related symptoms.

Subjects will be randomized to receive one of two different semi-scripted visit types – either a “standard visit” modeled after an empathic, conventional primary care evaluation or an “expanded visit” modeled after an integrative medicine consultation. During the visit, we will measure heart rate variability (HRV) and galvanic skin response (GSR) in the patient-provider dyads; in addition, we will video record the interactions for later

analysis of behavioral responses. Subjects will receive a two-month supply of amitriptyline (10 mg/day) or omeprazole (20 mg/day, depending upon the nature of their GERD symptoms), along with instructions for taking it. Following the visit, subjects will complete questions assessing their relationship/rapport with the study provider. Subjects will complete a daily GERD symptom diary during the first and eighth weeks of the study. At the end of the 8-week observation period, they will complete follow-up measures of GERD symptom severity and quality of life.

Interventions and Duration

Subjects will have a single visit with a “study provider,” a physician or nurse practitioner who they have never previously met. Subjects will complete a daily symptom diary for the 1st and 8th weeks following this visit and return for a second study visit in which they will complete questionnaires and be debriefed by a member of the study team.

Sample Size and Population

We plan to enroll 60 subjects with functional GERD, age 24-70 with heartburn symptoms 3 or more days per week. Thirty subjects will be randomized to the expanded visit intervention and 30 subjects will be randomized to the standard visit intervention (1:1 expanded vs. standard randomization). We will also enroll approximately 5-6 physicians or nurse practitioners and stratify randomization by study provider such that each provider will see 10-12 subjects (5-6 expanded visits and 5-6 standard visits).

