generally regarded as the most effective of these therapies and is generally used as an initial treatment for patients who first present with GERD symptoms. Nonetheless, many patients experience continued symptoms despite taking PPIs³⁰. Many patients who do not find relief with PPIs have functional heartburn symptoms and/or co-occurring dyspepsia symptoms (e.g., upper abdominal discomfort, bloating, and gas) that do not respond well to this class of medication^{31,32}. Moreover, awareness of the interconnections between the central nervous and gastrointestinal systems has led to the recognition that stress can profoundly affect gastrointestinal (GI) symptoms, such as GERD³³, suggesting that interventions targeting these pathways may improve symptoms³⁴. Notably, the placebo response rate in trials of GERD medications can be as high as 40%³⁵.

Many individuals with GERD symptoms who do not respond to PPIs have functional heartburn which is defined as less than 4% acid exposure on pH manometry and esophageal hypersensitivity^{36,37}. These patients respond better to neuromodulators such as tricyclic antidepressants, serotonin reuptake inhibitors, gabapentin, and other agents.

Amitriptyline is a tricyclic antidepressant originally used to treat depression but now frequently prescribed in low doses to treat functional GERD-related symptoms as well as functional dyspepsia, irritable bowel, fibromyalgia, and interstitial cystitis as well as other pain-related conditions^{36,38}.

[figure not shown]
Omeprazole is a PPI that is used as a first line treatment for patients who initially present with GERD symptoms.

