3. STUDY DESIGN

Study design: Single-center, single-blind, randomized controlled trial

Primary outcome:

1. Change in the average daily GERD symptom severity score from baseline to the last week of the study in the expanded vs. standard group. GERD symptom severity is based on the sum of scores assessing the severity of daytime heartburn, nighttime heartburn, and acid reflux each on a 0-4 point scale (none, mild, moderate, severe, very severe; higher scores signify worse symptoms).

Secondary outcomes:

1. Ratio of the sum of positive correlations over the sum of negative correlations in GSR (or HRV) across patient-provider encounters for standard vs. expanded visit types and for responders vs. non-responders (those with a 50% or greater improvement in their GERD symptom severity).
2. Absolute change in GSR (or high frequency HRV signal) in patient recordings from the beginning of the study visit to the end of the study visit and correlation with subsequent change in GERD symptom severity.
3. Differences in blinded ratings of 2 minute thin slices of study visit videos from the beginning to the end of the study in supportive global impressions (e.g., engagement, relaxed, patient seems pleased/satisfied) and non-verbal behaviors (e.g., smiling) between standard and expanded visit types and correlation with subsequent change in GERD symptom severity.

Study population:

Men and women age 24-70 with heartburn symptoms 3 or more days per week not responsive to proton pump inhibitors or with known functional heartburn. We will enroll until we reach 60 completing subjects.

Study location:

University of California Davis Medical Center

Length of subject participation: 8 weeks

Length of study enrollment: 2 years

Groups:

- 1) Standard visit (n=30), modeled after an empathic, high quality conventional primary care visit.
- 2) Expanded visit (n=30), modeled after a visit with an integrative medicine provider

Randomization:

The randomization code will be generated by the study statistician as described below (sections 4.3 and 9.2). The study will be single-blinded (study providers and the research team will know what the subject is receiving but the subject will not). Randomization will be stratified based on study provider. We anticipate 5 or 6 providers each seeing 10-12 subjects (5-6 standard visits, 5-6 expanded visits).

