4. SELECTION AND ENROLLMENT OF PARTICIPANTS

4.1 Inclusion Criteria

Research subjects eligible to receive amitriptyline must meet all of the following inclusion criteria to participate in the study:

- Adults ages 24-70 years old (rationale: population of interest, GERD frequency increases with age; amitriptyline is not recommended in older adults and may have increased risk of suicidality in adults younger than 24)
- Functional heartburn (defined as <4% of time with reflux on 24 hour pH manometry) symptoms 3 or more days per week with an average daily symptom severity of 3 or more on a 7-day baseline symptom diary (see section 6.2.2 for description of instrument; rationale: subjects must be symptomatic enough that improvement in symptoms is detectable. This threshold is similar to that seen in my pilot study⁶⁴).
- English language proficiency (rationale: feasibility)
- Willingness to be videotaped and connected to physiologic monitoring devices during the visit (rationale: feasibility/study procedures)
- Willingness to take amitriptyline daily for 8 weeks following study visit 1 (rationale: feasibility/study procedures)

Research subjects eligible to receive omeprazole must meet all of the following inclusion criteria to participate in the study:

- Adults age 24 and older
- Heartburn symptoms 3 or more days per week with an average daily symptom severity of 3 or more on a 7-day baseline symptom diary
- English language proficiency
- Willingness to be videotaped and connected to physiologic monitoring devices during the visit
- Willingness to take omeprazole daily for 8 weeks following study visit 1

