4.3 Study Enrollment Procedures

Patient Recruitment:

Initial recruitment efforts will start with the UC Davis Gastroenterology Clinic, and in particular, the motility disorders group. We will review scheduled patient visits and results from pH studies performed at the Midtown GI Clinic in EPIC. Patients identified as having typical GERD symptoms who have not yet tried a PPI or esophageal hypersensitivity will be contacted by [name] or their UCD gastroenterologist regarding their results and this study. The research team will contact the patient about the study only if the patient expresses interest and gives permission to the gastroenterologist to be contacted by the research team. If [name] is unable to reach the patient by phone, we will send the patient a letter in the mail or a MyChart message to inform them of the study.

Clinicians will also have copies of flyers they can hand to patients and the study research coordinator may also meet with some patients directly in the clinic. Study flyers may also be posted within the clinic. We may also recruit from primary care clinics. If a patient is interested in learning more about the study, they may request additional information during their appointment or may call the phone number on the flyer. Providers may also obtain verbal permission to give their prospective subjects' contact information to a study staff member who can provide further details about the study. This information may be shared with study staff in the form of an Epic patient list. We will also recruit using Study Pages and may use similar electronic recruiting platforms.

We will also recruit patients from the UCD Otolaryngology Reflux Clinic using procedures similar to those described above.

Patient Screening:

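### Study drug, settled before randomisation, is left out of the primary ANCOVA: the test is valid, and pre-specifying drug is a low-priority step that may sharpen it

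*Combined protocol and SAP*

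**What the plan says.** The primary model appears twice, with the same two terms. Section 9.5.1 reads "We will use ANCOVA for the primary analysis, adjusting for baseline GERD symptom severity and visit type assignment", with the 8-week score as outcome. The table in section 9.5 reads "ANCOVA analysis adjusting for baseline GERD symptom severity and visit type using follow-up GERD symptoms as the outcome". Neither has a term for drug. Provider is the only randomisation stratum (sections 4.3 and 9.2). Drug is not among the moderators named in section 9.5.1, although that list is not worded as closed, and it is not in section 9.6.

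The trial uses two drugs. The Précis gives the aim as testing whether the visit "can augment the effects of a medication targeting traditional or functional GERD symptoms", with subjects receiving "amitriptyline (10 mg/day) or omeprazole (20 mg/day, depending upon the nature of their GERD symptoms". Section 4.3 ties the drug to diagnosis and treatment plan, and the consent discussion covers the drug suited to the subject's condition. Sections 4.1 and 4.2 set separate criteria for each drug; the second inclusion list begins "Research subjects eligible to receive omeprazole must meet all of the following inclusion criteria". Appendix B labels the two pre-screening scripts as substudies. Randomisation follows consent, immediately before the provider visit (sections 4.3 and 6.2.3). Section 9.1 then pools both drug groups in one primary comparison.

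**The concern.** Drug is a baseline characteristic. Each inclusion list requires willingness to take that particular drug, so the choice must be made before enrolment. Visit type cannot change it: providers may not give their own treatment recommendations (section 4.3), and the medication advice is scripted identically in both arms (section 5.1).

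The documents also suggest that the two groups may follow different courses. One recruitment target in section 4.3 is "Patients identified as having typical GERD symptoms who have not yet tried a PPI". The population in section 3 is described as "not responsive to proton pump inhibitors or with known functional heartburn". Amitriptyline candidates need functional heartburn on pH testing; omeprazole candidates have no pH criterion.

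If 8-week scores differ between the drug groups after baseline adjustment, that difference stays in the residual and widens the interval for the visit effect. Because drug is not a stratum, its share can also differ between arms by chance. What is at stake is precision in a trial of 60 subjects.

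**Working it through.** **Inputs from the documents (section 9.2).** 30 subjects per arm, 80% power, two-sided alpha 0.05; SD 1.5 / 2.0 / 2.5 with minimal detectable difference (MDD) 1.10 / 1.47 / 1.84.

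**Assumed inputs.** The share p on one drug (0.5, 0.25 or 0.1) and D, the drug difference in 8-week score given baseline (0 to 2 points). The documents give neither.

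**1. The plan's own figure.** Noncentral t with 58 df and standard error SD × sqrt(2/30). Power at the stated MDDs is 79.8 / 79.9 / 80.0%. The table reproduces.

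**2. Validity without drug.** In simulation at SD 2.0 (50:50 and 10:90 splits, D = 0 or 2), type I error was 4.9 to 5.1% with or without the drug term. In separate runs (50:50, D = 0, 1, 2) without drug, a true effect of 1.47 was estimated on average as 1.471 to 1.476. There is no bias and no inflation.

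**3. Formulas for precision.** Section 9.2 does not say whether its SDs include variation between drug groups, so both readings are needed.

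- Reading A, SD is within drug: residual SD without drug = sqrt(SD² + p(1-p)D²); with drug = SD.
- Reading B, SD already includes drug: residual SD without drug = SD; with drug = sqrt(SD² - p(1-p)D²).
- Fitting drug multiplies the variance by about 1 + 1/56 and takes the error df from 57 to 56.

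Example (reading A, SD 2.0, 50:50, D = 1). Without drug: sqrt(4 + 0.25) = 2.062, standard error 2.062 × sqrt(2/30) = 0.532, 1.47/0.532 = 2.76, power 77.5%. With drug: 2.0 × sqrt(57/56) = 2.018, standard error 0.521, 1.47/0.521 = 2.82, power 79.2%.

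**4. Break-even.** Setting SD²(1 + 1/56) = SD² + p(1-p)D² gives D = SD × sqrt((1/56) / (p(1-p))).

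| Split | SD 1.5 | SD 2.0 | SD 2.5 |
|---|---|---|---|
| 50:50 | 0.40 | 0.53 | 0.67 |
| 25:75 | 0.46 | 0.62 | 0.77 |
| 10:90 | 0.67 | 0.89 | 1.11 |

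This ignores the lost df. At SD 2.0 the simulated gain crosses zero at nearly the same places: about 0.6, 0.6 and 0.9 to 1.0.

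**5. Change in power at D = 1 from adding drug** (points, by the formulas in step 3, reading A / reading B).

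| Split | SD 1.5 | SD 2.0 | SD 2.5 |
|---|---|---|---|
| 50:50 | +3.6 / +3.8 | +1.7 / +1.8 | +0.8 / +0.9 |
| 25:75 | +2.5 / +2.6 | +1.1 / +1.2 | +0.4 / +0.5 |
| 10:90 | +0.8 / +0.9 | +0.2 / +0.2 | -0.2 / -0.1 |

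The largest simulated gain at D = 1 was +4.0 (reading B, SD 1.5, 50:50).

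**6. Simulated power at SD 2.0 and a true difference of 1.47**, without → with drug (%).

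| Split, reading | D = 0 | D = 0.5 | D = 1 | D = 2 |
|---|---|---|---|---|
| 50:50, A | 79.2→78.5 | 78.8→78.5 | 76.8→78.6 | 69.9→78.5 |
| 50:50, B | 79.4→78.6 | 79.1→79.0 | 79.0→80.9 | 79.0→88.7 |
| 10:90, A | 79.1→78.4 | 79.1→78.6 | 78.4→78.6 | 75.8→78.6 |
| 10:90, B | 79.4→78.6 | 79.2→78.7 | 79.4→79.5 | 79.6→82.6 |

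D = 2 exceeds every MDD in section 9.2 and serves only as an outer bound. At D = 0 the loss is about 0.7 point by formula and up to 0.9 in simulation.

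**7. Chance imbalance.** With 30 of 60 subjects on one drug, the between-arm difference in drug share has SD sqrt(0.25 × (60/59) × (2/30)) = 0.130, so its 95% range is about ±0.26. At D = 1 that moves a single trial's estimate by up to about 0.26 point. This is part of the sampling variance already counted above, not a systematic bias.

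**The case against.** A two-term ANCOVA is a complete, pre-specified primary model, and adding further prognostic covariates is a matter of preference. That is right: nothing here is an error.

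The evidence that drug carries prognosis is thin. Section 2.1 says of PPI non-responders with functional heartburn: "These patients respond better to neuromodulators such as tricyclic antidepressants". That compares drugs within one type of patient. D compares functional patients on amitriptyline with other patients on omeprazole, and matching drug to condition could narrow that gap. Both lists require the same symptom frequency and severity threshold, and baseline severity is already in the model. This stands, and it is why the gain is only possible.

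Section 9.2 also tabulates SDs above the pilot value of 1.5. If the within-drug SD is 1.5, even D = 2 at 50:50 gives sqrt(2.25 + 1) = 1.80, inside the 2.0 row. Section 2.2 notes that many pilot subjects already took GERD medication, so the pilot SD may carry some of this variation. The reason given for a larger SD is the number of providers, but reading B is plausible, and under it the planned power is kept.

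A reader might infer that the drug mix confounds the visit comparison or invalidates the test. The documents do not support this, because drug is settled first and visit type is then randomised. Nor do they support calling the trial underpowered, since neither the split nor D is stated.

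Provider, the stratification factor, is also absent from the model. That is a separate point.

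**Conclusion.** The omission is real, and drug is a legitimate baseline covariate. The planned analysis is nevertheless valid and unbiased, and no stated figure is wrong. What remains is a possible loss of precision that the documents can neither establish nor exclude. Under the assumed splits and the tabulated SDs, adding drug gains little or nothing unless the groups differ by more than about 0.4 to 1.1 points after baseline adjustment. Gains much above 4 power points need a difference well above 1 point. The trade is modestly favourable because the downside is under 1 power point. This is an optional, low-priority improvement.

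**What to change.** In section 9.5.1 and the section 9.5 table, add study drug (amitriptyline or omeprazole, as chosen before randomisation) as a fixed covariate beside baseline severity and visit type. State that it is kept whatever split is observed, so that the choice is not driven by the data. Record the pre-randomisation drug choice from the eligibility and consent record, because the schedule in section 6.1 has no item for it. Sample size, randomisation and treatment do not change.

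The cost is a protocol wording change, which needs IRB review under section 11.1, one degree of freedom, and under 1 power point if drug is not prognostic.

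A drug by visit type interaction could be listed as exploratory, but the fix does not need it. At SD 2.0 the interaction detectable with 80% power is about 2.9 / 3.4 / 4.9 points at 50:50 / 25:75 / 10:90, so it should be labelled low-powered.

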To avoid alerting subjects to the fact that we are directly studying the effect of the patient-provider relationship on health outcomes (which could influence study results^{69,70}), subjects will be told during the consent process that 1) we are studying the relationship between their symptoms, their physiology, and their response to amitriptyline or omeprazole and 2) we are studying whether physicians mirror patients' physiology as has been suggested by some neuroimaging studies^{40,71} (to explain why providers are being similarly monitored). While it is challenging to study patient-provider interactions without subjects' direct knowledge, particularly since both are being monitored in this study, we believe that framing the study in this way is the most sensible way to proceed and the least likely to substantively affect the study's results. As the standard vs. expanded visit intervention is minimal risk, we believe it meets the federal criteria for modification of informed consent⁷², which allows us to conceal from participants that we are studying the patient-provider interaction.

Individuals who sign the informed consent document and elect to participate in the study will be considered enrolled. Only individuals who can provide informed consent will be eligible to participate.

Provider Recruitment and Screening:

We will advertise the study to primary care internal medicine and family medicine physicians and nurse practitioners via email. We may also recruit providers from the division of gastroenterology. We may also present the study at practice group meetings. Providers must be willing to adhere to the study protocol and not provide specific treatment recommendations (pharmacologic or non-pharmacologic) as this is outside the scope of the study. Providers must also be willing to receive a brief training to understand how to deliver the standard and expanded visit interventions.

Provider Consent:

Participating providers will be consented by the study PI. As study providers will deliver both visit interventions, they will be trained in both visit type formats. Providers will be notified of which intervention they are delivering immediately before walking into the room to conduct the study visit.

Randomization:

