Each study provider will participate in an orientation session to learn how to deliver the standard and expanded visit interventions. Providers will be explicitly instructed not to offer lifestyle treatment advice for GERD to maintain uniformity of the intervention across providers. The study PI will review video recordings of the interactions to offer feedback to study providers and ensure protocol fidelity. As each study provider finishes his/her portion of the study, the PI will interview them to understand their experiences of the study, the two visit types, and their views on the doctor-patient relationship.

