- Interpersonal Reactivity Index (IRI) – a validated 28 item self-assessment of cognitive and affective components of empathy⁷⁸.
- NEO Five Factor Inventory (NEO-FFI) – a validated 60 item instrument that measures five major dimensions of personality: extraversion, neuroticism, agreeableness, conscientiousness, and openness to experience [73]. Some dimensions have been associated with response to enhanced patient-provider interactions in others' studies⁷⁷.
- Demographics and practice – will assess things such as age, gender, race/ethnicity, and clinical experience (see Appendix D).
- Current Stress Question – 1 item self-report measure of current stress level on a scale of 0 (no stress) to 10 (extreme stress). Study providers will complete this question immediately prior to each study subject visit.
- Perceived Stress Scale (PSS) – a widely used 10 item measure of perceived stress that has been shown to correlate with a variety of different health outcomes⁷⁵. Study providers will complete this questionnaire immediately prior to each study subject visit.
- Fatigue Scale – 1 item self-report measure of the current fatigue level on a scale of 0 (no fatigue) to 10 (extreme fatigue). Study providers will complete this question immediately prior to each study subject visit.
- Physician Satisfaction Questionnaire (PSQ) – 20 item self-report measure assessing physician satisfaction with the patient visit. This measure includes a global satisfaction question and 19 items assessing 4 other domains: satisfaction with the patient-physician relationship, with the data collection process, with the appropriateness of the use of time, and with the absence of excessive demands on the part of the patient. Study providers will complete this questionnaire immediately after each study visit⁷⁹.

Randomization

Subjects will be randomized on the day of their baseline visit (Visit 1) to receive either the standard or expanded visit with the specific provider that they are scheduled to see that day. We will stratify randomization by provider so that each provider does the same proportion of standard and expanded visits. Randomization will occur during or immediately after subjects have completed their baseline questionnaires, immediately prior to the study visit.

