9.2 Sample Size and Randomization

The combined standard deviation (root mean square error) in my pilot fellowship study was 1.5⁶⁴. We are conservatively assuming that this number will likely be larger in this study given the greater number of providers involved. Given 30 subjects in each group (n=60 total), 80% power, a two-sided significance test with alpha = 0.05, the minimal detectable difference (MDD) in GERD symptom severity scores between the standard and expanded groups given the estimated standard deviations (SD) is shown in the adjacent table. These MDD values are similar to those found in my fellowship study⁶⁴ and are clinically meaningful^{86,87}.

Minimal Detectable Difference Between Groups	
SD	MDD
1.5	1.10
2.0	1.47
2.5	1.84

Treatment Assignment Procedures

A randomization scheme will be devised before the start of the study by the study biostatistician who will retain the code and will be responsible for breaking the blind at the end of the study. We do not anticipate a need to break the blind during the study because we are not expecting serious adverse events to occur more frequently in one visit group than another. Randomization will be stratified by provider, with permuted block sizes of 2 and 4 with a goal to have 5-6 providers each see 10-12 subjects. If a provider cannot commit to this many visits, the study biostatistician may need to adjust the randomization scheme and we will consent additional providers.

The study biostatistician will enter the randomization scheme into REDCap and subjects will be randomized immediately prior to the study visit intervention.

If a subject drops out or is unable to complete the study, the statistician may need to rebalance the randomization scheme.

Subjects will be informed of their visit group assignment during the debriefing at the end of the second study visit.

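### The primary ANCOVA omits provider, the factor randomisation is stratified on, so the test is conservative and loses some power to the extent that providers differ in mean outcome

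*Combined protocol and SAP*

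**What the plan says.** Sections 3, 4.3, 6.2.3 and 9.2 all make provider the stratification factor. Section 9.2: "Randomization will be stratified by provider, with permuted block sizes of 2 and 4". Section 6.2.3 gives the purpose: "We will stratify randomization by provider so that each provider does the same proportion of standard and expanded visits". The aim is 5 to 6 providers with 10 to 12 subjects each. If a provider cannot take that many, the biostatistician "may need to adjust the randomization scheme and we will consent additional providers".

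The primary model is stated twice. Section 9.5.1 describes an ANCOVA "adjusting for baseline GERD symptom severity and visit type assignment using the 8 week follow-up GERD symptom severity as the outcome". The table in section 9.5 agrees: "ANCOVA analysis adjusting for baseline GERD symptom severity and visit type using follow-up GERD symptoms as the outcome". Neither names provider, and no other model in sections 9.5 to 9.6 includes provider identity as a fixed or random effect. The nearest terms in 9.5.1 are provider gender and the patient's perceived connection with the provider, both exploratory moderators.

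On the outcome SD, section 9.2 takes 1.5 from the pilot and adds: "We are conservatively assuming that this number will likely be larger in this study given the greater number of providers involved".

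**The concern.** The design and the analysis do not match. Stratifying by provider keeps the two visit types nearly balanced within each provider, so a provider whose patients do better or worse on average affects both arms almost equally and adds little to the error of the visit comparison. A model without provider does not use this. It counts provider differences as residual noise and reports a standard error larger than the true sampling variability.

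The plan itself expects provider variation, since section 9.2 gives the number of providers as the reason for a larger SD. Section 4.3 also allows a mixed pool of internal medicine and family medicine physicians and nurse practitioners, and "We may also recruit providers from the division of gastroenterology".

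At stake is precision in a 60-subject trial sized at 80% power. If providers differ, the primary confidence interval is wider than the design requires and a real effect is more easily missed.

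**Working it through.** **Inputs from the plan (sections 3 and 9.2).** 30 per arm, two-sided alpha 0.05, 80% power, pilot SD 1.5, blocks of 2 and 4 within provider, 5 to 6 providers with 10 to 12 subjects each.

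**Assumptions, not in the documents.** The provider share of the variance left after baseline adjustment: 0, 5, 10, 20 and 44%. Also a baseline SD of 1.5 with slope 0.5, and a visit effect that is the same for all providers.

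**1. The plan's own figures.** The standard error is SD × √(2/30): 0.387, 0.516 and 0.645 for SD 1.5, 2.0 and 2.5. Solving the noncentral t (58 df) for 80% power gives MDDs of 1.103, 1.471 and 1.839. These match the table's 1.10, 1.47 and 1.84.

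**2. Why the standard error is overstated.** Take a within-provider variance of 1.5² = 2.25 and a provider variance P. With balance inside providers, the true variance of the visit effect is about 2.25 × 2/30 = 0.15, an SD of 0.387, whatever P is. For 5 providers of 12, the model without provider has an expected residual variance of about 2.25 + P × 12 × 4/57. Its reported standard error is about the square root of that figure divided by 15:

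- P = 0.118, share 0.118/2.368 = 5%: √(2.349/15) = 0.396
- P = 0.25, share 0.25/2.50 = 10%: √(2.461/15) = 0.405
- P = 0.5625, share 0.5625/2.8125 = 20%: √(2.724/15) = 0.426
- P = 1.75, share 1.75/4.00 = 44%: √(3.724/15) = 0.498

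The 44% case is an upper bound: provider main effects alone raise the SD from 1.5 to 2.0.

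**3. Simulation.** 5 providers × 12, residual SD 1.5, true difference 1.10, 6,000 trials per cell:

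| Provider share | Mean reported SE without provider | Power without | Power with | Type I error without |
|---|---|---|---|---|
| 0% | 0.390 | 78.6% | 78.5% | 5.0% |
| 5% | 0.397 | 78.0% | 78.9% | 4.7% |
| 10% | 0.407 | 76.5% | 79.1% | 4.5% |
| 20% | 0.426 | 72.5% | 78.6% | 3.9% |
| 44% | 0.494 | 61.1% | 79.4% | 2.0% |

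The true sampling SD was 0.39 to 0.40 throughout. With provider in the model, the mean reported standard error was 0.389 to 0.390. The mean estimate was 1.10 to 1.11 in every cell, so there is no bias. Type I error with provider is 5% in theory and 4.7 to 5.7% in simulation. Monte Carlo error is about 0.3 points for type I error and 0.5 to 0.6 points for power. With 6 providers × 10, power without and with provider was 76.6% and 79.0% at a 10% share, and 73.9% and 79.7% at 20%.

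**4. Total SD held at 2.0, difference 1.47 (a row of the plan's table).** 6 providers × 10, 10,000 trials per setting, power without and with provider:

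- share 0%: 79.2% and 78.7%
- 5%: 80.6% and 81.4%
- 10%: 81.1% and 82.8%
- 20%: 82.3% and 87.0%
- 30%: 84.1% and 90.7%

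Here the planned model stays near or above its 80% target, and the forgone gain is about 1, 2, 5 and 7 points at shares of 5, 10, 20 and 30%. With 15% random dropout and provider omitted, type I error was 4.4% at a 10% share and 4.0% at 20%, so the test remained conservative.

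**5. Cost of the term.** The planned model has 60 − 3 = 57 residual df. Provider takes 4 (5 providers), 5 (6 providers) or 9 (10 providers), leaving 53, 52 or 48. At SD 1.5 the MDD moves from 1.104 to 1.105, 1.106 or 1.107. With 10 providers × 6 and no provider variance, simulated power falls from 78.5% to 77.8%.

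**The case against.** The strongest reply is that nothing in the plan is wrong: a positive result would be valid, the 80% power stands for a given total SD, and the change only adds precision. That is correct, and it limits this to an efficiency point.

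The size also depends on a provider variance the documents do not give, and section 5.1 works to keep it small through scripted questions, identical medication advice, instructions on equal empathy, orientation and video feedback. For example: "Providers will be explicitly instructed not to offer lifestyle treatment advice for GERD to maintain uniformity of the intervention across providers". At shares of 5 to 10% the gain is only about 1 to 3 points. The 44% case assigns the whole rise in SD to provider means, which section 9.2 does not claim, so it should be read only as a bound.

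The framing matters too. Adding provider variance on top of SD 1.5 while keeping the difference at 1.10 makes the planned model appear to miss 80%, whereas section 9.2 already pairs larger SDs with larger differences. Step 4 shows the planned model then holds its target. The gain from adding provider remains under both framings.

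One caution stands. If the visit effect itself varies between providers and inference is meant for a wider population of providers, neither model is conservative, and the fixed provider term makes matters slightly worse. For assumed interaction SDs of 0.5 and 1.0 (6 × 10, 10% share), type I error was 5.9% and 9.7% without the term and 7.1% and 11.8% with it. That is a separate question and does not justify leaving out the stratification factor.

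**Conclusion.** The concern holds and should be fixed. Both statements of the primary model omit the stratification factor and nothing elsewhere supplies it. The result is a conservative test when provider means differ, and no loss when they do not. The likely loss is 0 to 3 power points for provider shares of 0 to 10% and about 5 to 6 points at 20%. About 18 points is an upper bound only. These figures assume provider differences in mean outcome with a common visit effect, at provider shares the documents neither give nor exclude. Validity is not threatened.

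**What to change.** In section 9.5.1 and the section 9.5 table, specify the primary analysis as an ANCOVA of the 8-week severity score on visit type, baseline severity and provider as a fixed effect. Before unblinding, state how providers with very few subjects, or with only one visit type, will be pooled, because section 9.2 allows providers to be added with fewer visits. Use the same provider term in the secondary ANCOVAs (GERD-HRQL, PROMIS GERD, GSRS).

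The term must be prespecified: adding it after unblinding would make the choice of primary model data-dependent. The text should also say that the provider main effect does not address visit effects that vary between providers.

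The cost is a change of wording, the pooling rule, and 4 to 5 degrees of freedom with 5 to 6 providers (more if providers are added). If providers do not differ at all, the power lost is under one point.
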